#### **6.4.1.3.6 SUPPORTIVE MANAGEMENT RECOMMENDATIONS FOR STOMATITIS, PALMAR-PLANTAR ERYTHRODYSÆSTHESIA SYNDROME, AND NAIL TOXICITY**

---

Stomatitis (35%), palmar-plantar erythrodysæsthesia syndrome (12%), and nail toxicity (eg, nail disorder [11%], nail discoloration [7%], and paronychia [4%]) are very commonly reported with infigratinib use. Management of these types of events should be considered, and treatment should follow institutional guidelines where applicable. ([QED 2019](#))

## 7 STUDY INTERVENTION DISCONTINUATION AND PARTICIPANT DISCONTINUATION / WITHDRAWAL

### 7.1 DISCONTINUATION OF STUDY INTERVENTION

Discontinuation from treatment does not mean discontinuation from the study, and remaining study procedures should be completed as indicated by the study protocol. If a clinically significant finding is identified (including, but not limited to changes from baseline) after enrollment, the investigator or qualified designee will determine if any change in participant management is needed. Any new clinically relevant finding will be reported as an adverse event (AE).

The data to be collected at the time of study intervention discontinuation will include the end-of-study (EOS) procedures as shown in Section 1.2.

### 7.2 PARTICIPANT DISCONTINUATION/WITHDRAWAL FROM THE STUDY

Participants are free to withdraw from participation in the study at any time upon request.

An investigator may discontinue or withdraw a participant from the study for the following reasons:

- Pregnancy
- Significant study intervention non-compliance
- If any clinical adverse event (AE), laboratory abnormality, or other medical condition or situation occurs such that continued participation in the study would not be in the best interest of the participant
- Disease progression which requires discontinuation of the study intervention
- If the participant meets an exclusion criterion (either newly developed or not previously recognized) that precludes further study participation
- Participant unable to receive study intervention for >28 days
- Participant has had 2 dose reductions and experiences an AE that would cause a third dose reduction.

The reason for participant discontinuation or withdrawal from the study will be recorded on the Case Report Form (CRF). Participants who sign the informed consent form and but do not receive the study intervention may be replaced. Participants who sign the informed consent form, and receive the study intervention, and subsequently withdraw, or are withdrawn or discontinued from the study, may be replaced.

### 7.3 LOST TO FOLLOW-UP

A participant will be considered lost to follow-up if he or she fails to return for the Expansion Cohort for 4 scheduled visits and is unable to be contacted by the study site staff.

The following actions may be taken if a participant fails to return to the clinic for a required study visit:

- The site will attempt to contact the participant and reschedule the missed visit within ~1 day of the missed visit and counsel the participant on the importance of maintaining the assigned visit schedule and ascertain if the participant wishes to and/or should continue in the study.
- Before a participant is deemed lost to follow-up, the investigator or designee will make every effort to regain contact with the participant (where possible, 3 telephone calls and, if necessary,

A Phase 0 Study of Infigratinib in Recurrent Glioblastoma Patients  
Protocol 2020-08

a certified letter to the participant's last known mailing address or local equivalent methods). These contact attempts should be documented in the participant's medical record or study file.

- Should the participant continue to be unreachable, he or she will be considered to have withdrawn from the study with a primary reason of lost to follow-up.

## 8 STUDY ASSESSMENTS AND PROCEDURES

### 8.1 EFFICACY ASSESSMENTS

#### 8.1.1 PHARMACOKINETIC (PK) MEASUREMENTS

The total and unbound concentrations of infigratinib in plasma, CSF, and tumor tissues (including contrast-enhancing and non-enhancing regions) will be determined by a validated LC-MS/MS method. All analyses will be performed at the Ivy Brain Tumor Center.

See the Ivy Brain Tumor Center Laboratory Manual for details regarding collection, processing, packaging and shipment.

##### 8.1.1.1 PK BLOOD SAMPLES COLLECTION

Participants will donate approximately a total of fifteen 4mL blood samples (approximately 60mL of blood) as noted in Section 1.2. If intravenous vein (IV) blood collection is utilized, the approximate total volume of blood will be 120mL of blood. Venipuncture may cause some pain, bleeding or bruising where the needle entered the participant's body. Some participants may have an intravenous (IV) catheter placed or a midline catheter for blood collection, as determined needed by the investigator. Placing an IV may cause some pain, and bleeding or bruising at the spot where the needle entered the participant's body. There may also be a risk of irritation of the vein (phlebitis), infection, blood clot, leakage or infiltration and/or nerve or tendon injury during insertion. Care will be taken to avoid these problems. The longer an IV catheter is left in place, the more common it is for redness or infection to develop. This information will be included in the participant informed consent and discussed with the participant as needed

##### 8.1.1.2 PK CSF SAMPLE COLLECTION

Approximately 1 mL of CSF from the resection cavity will be collected. Lumbar punctures are not considered necessary for CSF collection.

##### 8.1.1.3 PK TUMOR SAMPLES COLLECTION

Approximately 200mg of contrast-enhancing and 200mg of non-enhancing tumor tissue samples will be collected.

### 8.1.2 PHARMACODYNAMIC (PD) MEASUREMENTS

See the Ivy Brain Tumor Center Laboratory Manual for additional details regarding collection, processing, packaging and shipment.

##### 8.1.2.1 HISTORICAL/ARCHIVAL TISSUE SAMPLE COLLECTION

Archival or biopsy tissue testing to confirm eligibility may be conducted under this protocol or may also be conducted under the 2020-09 Data Tissue Screening Protocol, which received IRB approval on 06April2020. This protocol will collect available blood or tumor tissue from a previous or planned surgery in order to complete genetic and other tests to determine if the tumors indicate a match to one of the open clinical trial protocols, including Ivy 2020-08. If the tumor is a match to this study, the participant will be consented for participation into Ivy 2020-08.

## A Phase 0 Study of Infigratinib in Recurrent Glioblastoma Patients Protocol 2020-08

The archival tissue or biopsy tissue obtained through the Data and Tissue Screening Protocol will be stored at the Ivy Brain Tumor Center and used for the PD/Biomarker evaluation as noted in the Ivy 2020-08 Protocol.

If tissue testing is not conducted under the 2020-09 Data Tissue Screening Protocol, pretreatment archival tissue samples from a prior resection or biopsy tissue from either the current or prior recurrence will be requested to evaluate for PD and biomarkers to determine study eligibility after obtaining informed consent. Archival/biopsy tissue will be requested from pathology lab.

Request will be for approximately 3-10-micron sections of archival tissue FFPE blocks which contain > 3 mm x 3 mm portions of viable tumor, on 20 unstained slides, a representative H & E slide from this tissue, and 12 scrolls of 20-micron thickness of the pathology core tissue for (2 scrolls per 2 ml tube), if there is adequate tissue available. In the event when biopsy tissue is available, FFPE block of the needle biopsy and fresh-frozen tumor core biopsy will be requested. FFPE block will be processed to obtain 3-10 micron sections of 20 unstained slides and one H & E slide. The frozen tissue will be used for NGS analysis. Adjustments to the request may be made based on the available tissue. If adjustments are necessary, the decision should be made in conjunction with the nursing team, pathology lab and research lab.

### 8.1.2.2 INTRAOPERATIVE TISSUE SAMPLE COLLECTION

Post-treatment surgical tissue should be placed in formalin until taken to hospital histology lab where it will be prepared as a FFPE block (see Ivy Brain Tumor Center Laboratory Manual for tissue fixation protocol) and then made into approximately 3-10-micron sections of 20 unstained slides plus one H & E slide and 12 scrolls of 20-micron thickness of the pathology core tissue for (2 scrolls per 2 ml tube), if there is adequate tissue available.

The H&E slide will be examined by neuropathologist to confirm the presence of >20% of viable tumor in the resected tissue before proceeding with PD analysis.

In addition, one tumor sample (dimensions, 0.5 cm^3) will be collected from participants and divided into two equal portions.

### 8.1.2.3 PD EVALUATION IN TUMOR TISSUE

Identification of a positive PD effect (as defined by a significantly >30% decrease in the percentage of phospho-ERK+ cells) will be based upon comparative analysis of archival, biopsy (if available) and post-treatment tumor tissue. Immunohistochemistry (IHC) analysis will be used to identify the % positive cells of pERK, cleaved caspase 3 and MIB-1 (ki67) in archival versus infigratinib treated high-grade glioma tissue samples. The staining and biomarker positive cells will be quantified using Aperio Brightfield Toolbox Software available at Ivy Brain Tumor Center Pharmacodynamics and Pharmacokinetics Core at Barrow Neurological Institute. Optionally, western blotting will be performed for pERK, cleaved caspase 3 and MIB-1 on frozen treated tumor tissue and analyzed using the LiCOR Odyssey Imaging system. For comparison, treatment naïve tumor tissue with similar pathology from the Biobank will be used. The normalized average staining and/or luminescence for banked treatment naïve tumor will be used as a baseline to determine the pharmacodynamics of FGFR inhibition in the treated tumor tissues.

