### 3 OBJECTIVES AND ENDPOINTS

Objectives & Endpoints:	Objectives	Endpoints
Primary	1. Phase 0: To measure the pharmacokinetic (PK) effects of infigratinib in recurrent high-grade glioma participants.	1. Phase 0: Total and Unbound infigratinib concentration in enhancing and non-enhancing tumor tissue (8hr), plasma (0-24H) and CSF (8hr) will be determined.
	2. Expansion Cohort: Examine progression-free survival in recurrent high-grade glioma participants with demonstrated PK effects	2. Expansion Cohort: 6-month Progression-free survival (PFS6) rate from time of surgery to date of recurrence
Secondary	1. Phase 0: PD Analysis	1. Phase 0: percentage of pERK+, MIB-1+ and Cleaved Caspase 3+ cells from the surgical tissue will be quantified and compared to baseline archival/biopsy tissue.
	2. Expansion cohort: To monitor safety and tolerability of study drug combinations in participants with recurrent high-grade glioma.	2. Expansion Cohort: Safety and tolerability: 
 
a. Drug-related toxicity
 
b. Number of Adverse Events through study completion, assessed up to 60 months
 
c. Treatment-emergent adverse events (TEAEs)
 
d. Deaths
 
e. Clinical laboratory abnormalities per CTCAE (Version 5.0)
 

Exploratory	1. Phase 0: Describe systemic PK	1. Phase 0: Systemic plasma PK profile parameters ( $T_{max}$ , $C_{max}$ , $t_{1/2}$ , $AUC_{0-24h}$ ) for total and unbound levels will be determined for infigratinib.
	2. Expansion cohort: Examine Overall Survival (OS) in recurrent high-grade glioma participants with demonstrated PK effects	2. Median Overall Survival (OS) from time of surgery to date of death from any cause

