## 4 STUDY DESIGN

### 4.1 OVERALL DESIGN

This trial is an open-label, multicenter, Phase 0 trial that will enroll up to 20 participants with recurrent high-grade glioma (HGG) with FGFR1 K656E or FGFR3 K650E mutation or FGFR3-TACC3 translocation which are schedule for resection. In the lead-in cohort, a total of 20 HGG participants will be enrolled into the proposed phase 0 clinical trial. Participants will be administered infigratinib prior to surgical resection of their tumor.

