## 9 STATISTICAL CONSIDERATIONS

### 9.1 STATISTICAL HYPOTHESES

The phase 0 study will be conducted as an open-label, multi-institution study (up to 3 sites) with 20 patients in the phase 0 component and progression-free-survival (PFS) determination in the expansion cohort. The clinical trial will be considered an exploratory study to study the PK and PD effect of infigratinib from intra-operative tumor tissue and no formal statistical comparison or hypotheses will be carried out. Thus, the outcome will be summarized with descriptive statistics (N, median, mean, standard deviation, minimum, maximum and the 80% of confidence interval [CI] for the mean). The 80% confidence level is appropriate for a phase 0 study with small sample size.

If, after the study has begun, changes are made to primary and/or key secondary hypotheses, or the statistical methods related to those hypotheses, then the protocol will be amended. Changes to exploratory or other non-confirmatory analyses made after the protocol has been finalized, along with an explanation as to when and why they occurred, will be listed in results for the study. Post hoc exploratory analyses will be clearly identified. No separate Statistical Analysis Plan (SAP) will be issued for this study.

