### 9.3 POPULATIONS FOR ANALYSES

- Safety Analysis Dataset: participants who took at least one dose of study intervention
- PK Analysis Dataset: All participants who undergo surgery and are assessed for the PK endpoint in Phase 0
- Efficacy Analysis Dataset: The subset of participants who meet the PK criteria in Phase 0 and begin at least one day of treatment on Expansion Cohort.
- PD Analysis Dataset: All participants with evaluable PD data assessable for the PD secondary endpoints

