### 9.4.2 ANALYSIS OF THE SECONDARY ENDPOINT(S)

PD Analysis: To compare pharmacodynamics biomarkers, paired archival, biopsy (if available) and surgical tissue will be examined. Once the percentage of individual biomarker positive cells was quantified, a paired t test will be used to compare log-transformed percent positive cells between archival, biopsy (if available) and surgical tissue at a 2-sided 5% level.

Safety Analyses: All adverse events will be tabulated according to the highest grade observed per patient for each event or category. Tabulations (n and %) will be produced for each of the following categories: Clinical laboratory abnormalities will be coded per CTCAE (Version 5.0)

- a. All treatment-emergent Adverse Events
- b. Treatment related Adverse Events (defined as those definitely, probably, or potentially related to treatment)
- c. Serious Adverse Events

---

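### The planned paired t test neither tests the 30% pERK threshold that defines a positive PD effect nor classifies participants

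*Combined protocol and SAP*

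**What the plan says.** Section 8.1.2.3 makes a positive PD effect depend on a "significantly >30% decrease in the percentage of phospho-ERK+ cells", judged by comparing pre-treatment tissue with post-treatment tumor tissue. It does not say whether the criterion applies to a participant or to the group, or whether 30% is a relative fall or percentage points.

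Section 9.4.2 contains the only PD test: "a paired t test will be used to compare log-transformed percent positive cells between archival, biopsy (if available) and surgical tissue". The significance level is 5%, two-sided. The section gives no reference value, no rule for reading a confidence limit against a threshold, and no responder rule.

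The secondary endpoint in section 3 says only that pERK, MIB-1 and cleaved caspase 3 "will be quantified and compared to baseline archival/biopsy tissue". The 30% figure does not appear there, in the synopsis, or anywhere in section 9. Section 9.1 states that "no formal statistical comparison or hypotheses will be carried out" and rules out a separate SAP, so no other planned document supplies the link.

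**The concern.** A paired t test with no stated margin asks whether the mean log difference is zero, that is, whether the post/pre ratio is 1. The criterion in 8.1.2.3 concerns a fall of more than 30%, which is a ratio below 0.70 if the fall is relative. Rejecting a ratio of 1 does not show that the ratio is below 0.70.

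A per-participant reading does not close the gap. The background in section 2.1.1 treats PD positivity as a label on individual patients, separating biological responders from non-responders. A group t test labels nobody.

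What is at stake is the study's statement on target modulation. As written, the analyst would have to decide after seeing the data whether positive means p<0.05, an observed fall above 30%, both, or a count of participants.

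**Working it through.** The documents give no SD, power or assumed effect for the PD test, so there is no figure to reproduce.

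**Inputs from the documents**
- Threshold: a 30% fall (8.1.2.3). Taken as relative, the margin is ln 0.70 = −0.357.
- Test: paired t on log percentages, two-sided 5% (9.4.2).
- Pairs: at most 20, since "a total of 20 HGG participants will be enrolled into the proposed phase 0 clinical trial" (4.1). The PD set may be smaller, because 9.3 limits it to "All participants with evaluable PD data assessable for the PD secondary endpoints".

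**Assumption**
- SD of the within-participant log differences: 0.3 to 1.0.

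**Formulas**, with h = t(0.975, n−1) × SD/√n
- Smallest observed fall significant against no change: 1 − exp(−h).
- Smallest observed fall that excludes a true fall of 30% or less: 1 − exp(ln 0.70 − h).
- Chance of significance in the direction of a fall: lower tail of the noncentral t with n−1 degrees of freedom and noncentrality ln(true ratio)/(SD/√n).

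**Worked case, n = 20, SD 0.5**
- t(0.975, 19) = 2.093 and SD/√n = 0.5/√20 = 0.1118, so h = 0.234.
- Against no change: 1 − exp(−0.234) = 20.9%.
- Against 30%: 1 − 0.70 × exp(−0.234) = 44.6%.
- True fall of 20%: noncentrality ln 0.80/0.1118 = −2.00, chance of significance 47%.

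**Range at n = 20**

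| SD | Observed fall giving p<0.05 against no change | Observed fall needed to exclude ≤30% | Planned test significant, true fall 20% | Planned test significant, true fall exactly 30% |
|---|---|---|---|---|
| 0.3 | 13% | 39% | 88% | 99.9% |
| 0.5 | 21% | 45% | 47% | 86% |
| 0.8 | 31% | 52% | 22% | 47% |
| 1.0 | 37% | 56% | 16% | 33% |

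At a true fall of exactly 30% the criterion of more than 30% is not met. A test against 0.70 would then be significant in the direction of a larger fall 2.5% of the time.

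**When an observed fall below 30% can be significant.** Setting h = 0.357 gives SD = 0.357 × √n / t. This is about 0.76 at n = 20 and about 0.50 at n = 10 (t = 2.262). Above those SDs, significance itself requires an observed fall of more than 30%, but it still does not exclude a true fall of 30% or less.

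**The unwritten two-part rule** (significant against no change, and observed fall above 30%). Simulation at n = 20 with a true fall of exactly 30% gives a positive call in about 50%, 50%, 43% and 32% of trials at SD 0.3, 0.5, 0.8 and 1.0.

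**The case against.** The best defence is that the phrase in 8.1.2.3 can mean a decrease that is statistically significant and also larger than 30%. The 9.4.2 test would then cover the first half and the point estimate the second, and an observed 21% fall would fail despite p<0.05. That reading is possible, but the plan does not write it down. It would also leave a positive call likely at a true fall of exactly 30%.

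A reader might infer that the trial will declare a PD effect on p<0.05 alone, with a reduction short of 30%. The documents do not support that. Section 9.4.2 never equates significance with PD positivity, 8.1.2.3 itself requires more than 30%, and the null of no change is implied rather than stated. A test of no change also fits the threshold-free endpoint in section 3, so it has a legitimate use.

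A reader might also infer that a significance statement for one participant is impossible. That goes too far. Sections 8.1.2.1 and 8.1.2.2 ask for 20 unstained slides from the pre-treatment tissue and 20 from the surgical tissue, so replicate readings could be made. What is missing is any plan for a within-participant test.

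The dependence on an assumed SD, on the number of evaluable pairs and on a relative 30% is a fair limit. It changes the size of the gap; under either the group or the per-participant reading, the stated test still does not evaluate the stated criterion.

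**Conclusion.** The point holds as a mismatch between criterion and analysis: the one planned PD test does not address the 30% threshold and assigns no participant a PD status. Under the stated assumptions, the observed fall needed to support a claim of more than 30% exceeds the fall needed for p<0.05 by about 19 to 26 percentage points at n = 20 (56 − 37 at SD 1.0; 39 − 13 at SD 0.3).

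The consequence is limited to the secondary PD conclusion. Section 2.1.1 speaks of a trigger that depends on both PK and PD, so a reader might infer that an unclear PD rule could affect who enters the expansion cohort. The operative text does not support this: the synopsis, 4.1.2 and the efficacy set in 9.3 all use the PK criterion alone. The change should be made, but it does not threaten the primary endpoints.

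**What to change.** In 8.1.2.3 and 9.4.2:

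1. State whether 30% is a relative fall (ratio 0.70) or something else.
2. Per participant: define PD-positive as an observed pERK fall above 30%, delete the word that calls for significance, and report n/N with an exact CI. Name the one baseline used when both archival and biopsy tissue exist.
3. Group: report the geometric mean post/pre ratio with its CI. Keep the t test only as evidence of any change. Claim a group fall above 30% only if the upper confidence limit is below 0.70. State the confidence level: 95% would match the 5% test used in the figures here, whereas 9.1 uses 80% for descriptive summaries.
4. Reconcile 9.1, which disclaims formal comparison, with the 5% test in 9.4.2.

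This takes a few sentences and no new data. The cost is a stricter group claim with limited power. For a true 50% fall at n = 20, the noncentrality is (ln 0.50 − ln 0.70)/(SD/√20), which is −3.01 at SD 0.5. Power against 0.70 is about 81% at SD 0.5, 43% at SD 0.8 and 30% at SD 1.0; with 10 pairs and SD 0.5 it is 48%. The per-participant count is therefore likely to be the more useful summary if variability is high.

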### 8.1.2.4 BIOMARKER EVALUATION IN TUMOR TISSUE

To assess other biomarker changes in the treated tumor tissue, mRNA and/or protein from FFPE slides from pre- and post-treatment samples will be extracted and be analyzed by nanostring nCounter analysis system for their cancer panel examination or RNAseq analysis. This cancer panel includes key components

## A Phase 0 Study of Infigratinib in Recurrent Glioblastoma Patients Protocol 2020-08

in the oncogenic signaling pathways, cell cycle pathway, apoptosis pathways and immune cell profiling. This would allow comparison with surgical tissue with archival and/or biopsy tissue. Any promising targets will be confirmed with quantitative RT-PCR.

In addition, gliomas can be sub-classified by IHC or RNA sequencing as mesenchymal, proneural, or classical signatures based on the sequencing analysis and comparison to the TCGA database.

### 8.1.2.5 PD BLOOD COLLECTION

Participants will donate approximately a total of 4mL of blood as noted in Section 1.2. If intravenous vein (IV) blood collection is utilized, the approximate total volume of blood will be 8mL of blood. Plasma will be shipped to the IBTC for further testing.

See the Ivy Brain Tumor Center Laboratory Manual for details regarding collection, processing, packaging and shipment.

